#### 5.4.1.1 Sensitivity Analysis

The following analyses will be considered as sensitivity analyses:

- PP analysis: The same primary efficacy analyses described in [Section 5.4.1](#) will be repeated based on the PP analysis set.
- Observed case: The same primary efficacy analyses described in [Section 5.4.1](#) will be repeated based on observed data. Subjects with missing information about the primary efficacy outcome will be excluded from this analysis.
- Fisher's exact Test: The same primary efficacy analyses described in [Section 5.4.1](#) will be carried out using Fisher's exact test.
- Modified primary efficacy endpoint: Proportion of subjects who do not require a platelet transfusion after randomization and up to 7 days following an elective procedure. This efficacy endpoint will be analyzed using the same approach as primary efficacy analysis using FAS

Additional sensitivity analyses may also be explored, if deemed appropriate.

#### 5.4.1.2 Subgroup Analysis

The primary efficacy variable described in [Section 5.4.1](#) will be summarized by each subgroup listed below.

- age group (<65 and ≥65 years old)
- sex (male and female)
- race (white, black, Asian and other)
- geographic region
- bleeding risk associated with the elective procedure (low, moderate and high based on Amendment 02 categorization)
- MELD score (<10, 10-14, and >14)
- CTP grade (A, B, and C)
- Disease etiology (alcoholic liver disease, chronic viral disease, nonalcoholic steatohepatitis, other)

Additional subgroups may also be explored, if deemed appropriate.

#### 5.4.2 Secondary Efficacy Analyses

There are 2 secondary efficacy endpoints in this study:

- Proportion of responders, defined as subjects who achieve target platelet counts of  $\geq 50 \times 10^9/L$  on Procedure Day (prior to receiving a platelet transfusion or undergoing the elective procedure)
- Change from baseline in platelet count on Procedure Day (prior to receiving a platelet transfusion or undergoing the elective procedure)

The analysis of the secondary efficacy variables, as defined above, will proceed following a sequential gatekeeping testing procedure to control the family-wise Type I error rate at a significance level of  $\alpha=0.05$ .

##### 5.4.2.1 Proportion of subjects achieved platelet counts of $\geq 50 \times 10^9/L$ on the Procedure Day

The proportion of subjects who achieve platelet counts of  $\geq 50 \times 10^9/L$  on the Procedure Day will be analyzed first.

The proportion of subjects with platelet counts of  $\geq 50 \times 10^9/L$  on the Procedure Day will be tested between the individual avatrombopag treatment group (40 or 60mg) and matching placebo separately within each baseline platelet count cohort ( $< 40 \times 10^9/L$  or from 40 to  $< 50 \times 10^9/L$ ), each at a significance level of  $\alpha=0.05$  using the generalized CMH test adjusting for the risk of bleeding associated with the elective procedure (low, moderate, or high based on Amendment 02 categorization).

The 95% CI for the proportion of subjects with platelet counts of  $\geq 50 \times 10^9/L$  on the Procedure Day will be calculated for each treatment group within each baseline platelet count cohort. In addition, the 95% CI for the difference between avatrombopag and placebo will also be provided within each baseline platelet count cohort using normal approximation method.

Subjects with missing platelet count on Procedure Day will be considered as not achieving the platelet count of  $\geq 50 \times 10^9/L$  for this analysis.

##### 5.4.2.2 Change from baseline in platelet count on the Procedure Day

The second secondary efficacy variable, change from baseline in platelet count on the Procedure Day, will be analyzed only if the first secondary efficacy variable is statistically significant for both baseline platelet count cohorts.

The change from baseline in platelet count on Procedure Day will be analyzed using the Wilcoxon rank sum test separately within each baseline platelet count cohort ( $< 40 \times 10^9/L$  or from 40 to  $< 50 \times 10^9/L$ ), each at a significance level of  $\alpha=0.05$ . The treatment difference

between avatrombopag and placebo will be provided within each baseline platelet count cohort using Hodges-Lehmann estimation along with associated asymptotic (Moses) 95% CIs.

Last observation carried forward will be used for subjects with missing platelet count on Procedure Day for this analysis.

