9.4.3 Method of Assigning Subjects to Treatment Groups

Subjects will be enrolled into 2 cohorts according to mean baseline platelet count ($<40 \times 10^9/L$ or from 40 to $<50 \times 10^9/L$), with neither baseline platelet count cohort comprising greater than 55% of the total number of subjects enrolled into the study. Within each cohort, subjects will be further stratified centrally by risk of bleeding associated with the elective procedure (low, moderate, or high) and HCC status (Yes or No), in order to ensure balance between treatments within each cohort and each further stratum. Within each cohort and each further stratum, subjects will be assigned in a 2:1 ratio to receive avatrombopag or placebo once a day for 5 days

based on a computer-generated randomization scheme using permuted-block randomization. It is planned that no fewer than 10% of subjects will be enrolled into the high risk group and no more than 60% of subjects in the low-risk group. The randomization scheme and identification for each subject will be kept strictly confidential before the database lock and final unblinding, and will be included in the final clinical study report for this study.

Approximately 200 subjects who meet all the eligibility requirements will be randomized. (revised per Amendment 04)

Randomization will be performed centrally by an IxRS. The IxRS or clinical supply vendor will generate the randomized study drug identification numbers. After successful completion of Visit 1, the investigator or designee will call or access via web the IxRS to register the subject information and the IxRS will assign each subject a unique 6-digit randomization number at Visit 2.

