The proportion of subjects who achieve platelet counts of $\geq 50 \times 10^9/L$ on the Procedure Day will be analyzed first. The proportion of subjects with platelet counts of $\geq 50 \times 10^9/L$ on the Procedure Day will be tested between the individual avatrombopag treatment group (40 or 60 mg) and matching placebo separately within each baseline platelet count cohort ($< 40 \times 10^9/L$ or from 40 to $< 50 \times 10^9/L$), each at a significance level of $\alpha=0.05$, using the generalized CMH test adjusting for risk of bleeding associated with the elective procedure (low, moderate, or high based on Amendment 02 categorization).

The second secondary efficacy variable, change from baseline in platelet count on the Procedure Day, will be analyzed only if the test for the first secondary efficacy variable is statistically significant for both baseline platelet count cohorts. The change from baseline in platelet count will be analyzed using the Wilcoxon rank sum test separately within each baseline platelet count cohort ($< 40 \times 10^9/L$ or from 40 to $< 50 \times 10^9/L$), each at a significance level of $\alpha=0.05$.

(REVISED PER AMENDMENT 04)

EXPLORATORY EFFICACY ANALYSES

The following efficacy variables are considered exploratory:

- Platelet count and change from baseline in platelet count at each visit
- Proportion of subjects who achieve platelet count of $\geq 50 \times 10^9/L$, $\geq 75 \times 10^9/L$, or $\geq 200 \times 10^9/L$ at each visit
- Number of platelet units used per platelet transfusion episode
- Severity of bleeding events assessed by WHO bleeding score and BARC bleeding scale
- Proportion of subjects with a WHO bleeding score ≥ 2 after randomization and up to 7 days following an elective procedure (revised per Amendment 04)

In general, the continuous variables will be analyzed within an analysis of covariance framework or Wilcoxon rank sum test, as appropriate. Categorical variables will be analyzed using CMH, Chi-square or Fisher's exact test. Additional analysis may be performed as needed using appropriate statistical methodologies as specified in the SAP.

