### 5.4.1 Primary Efficacy Analyses

The primary efficacy variable is the proportion of subjects who do not require a platelet transfusion or any rescue procedure for bleeding after randomization and up to 7 days following an elective procedure.

The null hypothesis is that the proportion of subjects not requiring a platelet transfusion or any rescue procedure for bleeding after randomization and up to 7 days following an elective procedure is the same between the avatrombopag and placebo treatment groups. The corresponding alternative hypothesis is that the proportion of subjects not requiring a platelet transfusion or any rescue procedure for bleeding after randomization and up to 7 days following an elective procedure is not the same between avatrombopag and placebo. This hypothesis will be tested separately with each baseline platelet count cohort.

The proportion of subjects not requiring a platelet transfusion or any rescue procedure for bleeding will be tested between the individual avatrombopag treatment group (40 or 60mg) and matching placebo within each baseline platelet count cohort ( $<40 \times 10^9/L$  or from 40 to  $<50 \times 10^9/L$ ), each at a significance level of  $\alpha=0.05$  using the generalized Cochran Mantel Haenszel (CMH) test adjusting for the risk of bleeding associated with the elective procedure (low, moderate, or high based on Amendment 02 categorization).

- For subjects with platelet count  $<40 \times 10^9/L$  at baseline, the treatment comparison will be carried out between the 60 mg avatrombopag treatment group (Group A) versus matching placebo (Group B).
- For subjects with platelet count from 40 to  $<50 \times 10^9/L$  at baseline, the treatment comparison will be carried out between the 40 mg avatrombopag treatment group (Group C) versus matching placebo (Group D).

This study will be considered as positive if statistical significance is achieved for primary efficacy endpoints for both baseline platelet count cohorts.

The 95% CI for the proportion of subjects not requiring a platelet transfusion or any rescue procedure for bleeding will be calculated for each treatment group within each baseline platelet count cohort. In addition, the 95% CI for the difference between avatrombopag and matching placebo will also be provided within each baseline platelet count cohort using normal approximation method.

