Since the HCC status is included in the randomization stratification for safety purposes only, not for efficacy consideration, HCC will not be included in the CMH model for the primary efficacy analysis.

Subjects with missing information about the primary efficacy outcome due to early withdrawal or other reasons will be considered as having received a transfusion for the primary analysis.

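### The Wilcoxon test for the second secondary endpoint leaves out bleeding risk; it is valid, but it may lose precision if bleeding-risk category predicts platelet change

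*SAP*

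**What the plan says.** The second secondary endpoint is the change in platelet count from baseline to Procedure Day, measured before any transfusion and before the procedure. Protocol 9.7.1.6 states: "The change from baseline in platelet count will be analyzed using the Wilcoxon rank sum test". SAP 5.4.2.2 specifies the same "Wilcoxon rank sum test separately within each baseline platelet count cohort" and reports the treatment difference "using Hodges-Lehmann estimation along with associated asymptotic (Moses) 95% CIs". Neither names bleeding risk for this endpoint.

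Three other places treat bleeding risk differently:

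- Protocol 9.4.3, on randomisation: "Within each cohort, subjects will be further stratified centrally by risk of bleeding associated with the elective procedure". HCC status is the other stratification factor.
- SAP 5.4.1, primary endpoint: "generalized Cochran Mantel Haenszel (CMH) test adjusting for the risk of bleeding associated with the elective procedure".
- SAP 5.4.2.1, first secondary endpoint: "using the generalized CMH test adjusting for the risk of bleeding associated with the elective procedure".

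SAP 5.3.2 lists only the primary and first secondary endpoints as covariate-adjusted. The SAP gives a reason for omitting HCC ("HCC will not be included in the CMH model for the primary efficacy analysis", because it was stratified on for safety only). It gives none for omitting bleeding risk from the Wilcoxon test.

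**The concern.** The two secondary endpoints are two summaries of one measurement. Cut at 50 × 10⁹/L, the Procedure Day count is analysed with bleeding-risk adjustment; expressed as a change from baseline, it is not.

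Randomising within strata balances them between arms, so differences between strata add little real variability to the treatment comparison. An unstratified rank test still counts those differences as noise. If the strata predict the outcome, its null variance is too large, the type I error falls below 5%, power drops, and the confidence interval is wider than it need be. What is at stake is the precision of the third confirmatory comparison and of the reported platelet effect.

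**Working it through.** **The plan's own figure.** The only power statement, in protocol 9.7.2 and SAP section 4, is for the primary endpoint: above 90% per cohort with 67 versus 33 subjects, 53% versus 18%, Fisher's exact test, two-sided 0.05. Exact enumeration, summing the two binomial probabilities over all tables with p ≤ 0.05, gives 92.6%. The figure holds. No SD, effect size or power is given for platelet change, so the rest uses assumed values.

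**Inputs from the documents.** 100 subjects per cohort; 2:1 permuted blocks within strata; three risk levels crossed with HCC; at least 10% high risk and at most 60% low risk (planned over the whole study).

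**Assumed inputs.** Normal outcome; risk shares of 60/20/20 or 60/30/10; 30% with HCC; a constant step between adjacent risk strata of 0 to 1.0 SD (within-stratum SD); 6,000 runs per setting.

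**Tests.** With m active and k placebo subjects, N = m + k and ranks r:

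- Unstratified: Z = (W − E)/√V, where W is the active rank sum, E = m(N + 1)/2 and V = mk/[N(N − 1)] × Σ(r − r̄)².
- van Elteren: Z = Σ w_g(W_g − E_g)/√(Σ w_g²V_g) over the three risk strata, with w_g = 1/(n_g + 1).

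**How strong the assumed steps are.** Coding risk as −1, 0, 1 with shares 60/20/20, the variance is 0.80 − 0.40² = 0.64. A step of s SD therefore explains 0.64s²/(1 + 0.64s²) of the outcome variance: 3.8% at 0.25, 13.8% at 0.5 and 39.0% at 1.0.

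**Results for a 0.5 SD treatment effect** (unstratified / van Elteren, in %; gains from unrounded values):

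| Shares | Step (SD) | Power | Gain (points) | Type I error |
|---|---|---|---|---|
| 60/20/20 | 0 | 61.0 / 60.4 | −0.6 | 5.1 / 5.3 |
| | 0.25 | 60.6 / 61.0 | +0.5 | 4.6 / 4.8 |
| | 0.5 | 54.8 / 59.8 | +5.0 | 3.7 / 4.8 |
| | 1.0 | 41.4 / 61.6 | +20.2 | 1.6 / 4.9 |
| 60/30/10 | 0 | 62.4 / 62.1 | −0.3 | 5.4 / 5.3 |
| | 0.25 | 61.0 / 61.6 | +0.6 | 4.7 / 4.8 |
| | 0.5 | 59.8 / 62.9 | +3.0 | 4.3 / 5.1 |
| | 1.0 | 47.3 / 61.7 | +14.3 | 2.5 / 5.1 |

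The Monte Carlo standard error of a 5% rate is √(0.05 × 0.95/6000) = 0.28 points, so 5.4% is compatible with nominal.

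**Larger effect.** At 1.0 SD both tests exceed 97% power in every setting. The largest gain is 97.8% to 99.5%, under 2 points.

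**Interval.** In a further simulation of one cohort at a 1.0 SD effect (3,000 runs per setting), the unstratified interval was wider than the stratified one by 1%, 7% and 28% at steps of 0.25, 0.5 and 1.0 SD with shares 60/20/20, and by 0.4%, 4% and 20% with shares 60/30/10. With no step it was 1% narrower. At the 1.0 SD step with shares 60/20/20 its coverage was 98.6% against a nominal 95%. Stratified coverage stayed between 94.7% and 95.8%.

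**Cost when the strata do not matter.** The table shows 0.3 to 0.6 points lost. A second, independent simulation of the same kind put the loss at about 1 to 2 points, so 2 is a reasonable ceiling.

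**The case against.** The strongest objection is that no loss has been shown for this trial. The risk category is defined by procedure type and the count is taken before the procedure, so a strong direct link is not obvious. Steps of 0.5 to 1.0 SD put 1 to 2 SD between low and high risk, and nothing in the documents supports that size. This stands. The case for a link is indirect: the procedures in the risk table reflect different patients, for instance paracentesis against ablation for liver cancer. The same doubt applies to the first secondary endpoint, where the plan adjusts anyway.

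Second, the documents point to a large effect. On a normal latent scale, 18% versus 53% is 0.075 + 0.915 = 0.99 SD. The Phase 2 responder rates of 8.1% and 48.4% (protocol 7.1.2.3) give 1.398 − 0.040 = 1.36 SD. With an effect calibrated to 18% versus 53% at a platelet cut-off (an assumption), simulated power was at least 99.4% for both tests at every step. This also stands, for power. The wider interval remains.

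Third, the endpoint is tested only after the primary and first secondary endpoints succeed in both cohorts (SAP 5.3.3). In a simulation with a 0.65 SD effect and an assumed 18% placebo rate, power given that the first-secondary test had passed in the cohort was 96.9% unstratified versus 96.8% stratified with no step, 95.9% versus 96.8% at 0.5 SD, and 89.7% versus 96.2% at 1.0 SD. The gate therefore shrinks the practical gain.

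Fourth, analysing as randomised is not the plan's rule. HCC is also left out of the CMH tests, and the Amendment 02 categories may differ from the randomisation strata for subjects enrolled earlier. That weakens an argument from consistency alone, but not the efficiency argument.

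**Conclusion.** This is a minor point that holds conditionally. The plan omits, without a reason, a factor that it randomises on and adjusts for in the two tests ahead in the sequence, one of them on the same count.

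A reader might infer that the unstratified test is invalid. It is not: its error rate is at or below nominal, and it is pre-specified identically in both documents and paired with a matching estimate. A reader might also infer that precision is certainly given up for nothing. The documents do not support that either: they give no association between risk category and platelet change, and with no association the unstratified test is marginally the better one.

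The size depends on that unknown association and on the assumed effect. For a 0.5 SD effect, the loss is negligible for steps up to 0.25 SD, about 3 to 5 power points at 0.5 SD, and about 14 to 20 at 1.0 SD. For a 1.0 SD effect it is under 2 points, and what remains is a wider, over-covering interval if the strata are strongly prognostic. Against this, the cost of stratifying is at most about 1 to 2 points.

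**What to change.** Before unblinding, amend SAP 5.4.2.2, with 5.3.2 to match, to specify within each platelet cohort a van Elteren test stratified by the Amendment 02 bleeding-risk categories used in the CMH tests, and a stratified Hodges-Lehmann estimate with its confidence interval. Keep the unstratified Wilcoxon test and Moses interval as a sensitivity analysis. Protocol 9.7.1.6 names the unstratified test, so record the change under planned-analysis changes in SAP section 7. If the sponsor prefers the present test, one sentence giving the reason would be the minimum.

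The cost is a few lines of SAP text, a test available in standard software, some extra programming for the stratified interval, and the small power loss already noted if the strata are not prognostic. At the 10% high-risk minimum, a cohort of 100 would hold about 10 high-risk subjects, roughly 7 versus 3, if the shares are alike in both cohorts. Stratified coverage held up in that setting.

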### 5.4.3 Other Efficacy Analyses

The following efficacy analyses are for exploratory purpose only.

#### 5.4.3.1 Platelet count and change from baseline in platelet count at each visit

Platelet count and change from baseline in platelet count will be compared between individual avatrombopag (40 or 60mg) and matching placebo separately within each baseline platelet count cohort at a significance level of  $\alpha=0.05$ , using the Wilcoxon rank sum test based on observed data. Missing values will not be imputed.

#### 5.4.3.2 Proportion of responders defined as subjects who achieve platelet counts of $\geq 50 \times 10^9/L$ , $\geq 75 \times 10^9/L$ , or $\geq 200 \times 10^9/L$ at each visit

The number and percentage of responders will be summarized by treatment group within each baseline platelet count cohort at each visit. Missing values will not be imputed.

#### 5.4.3.3 Number of platelet units used per platelet transfusion episode

The average number of platelet units used per platelet transfusion episode will be summarized by treatment group within each baseline platelet count cohort using descriptive statistics for subjects require platelet transfusion.

#### 5.4.3.4 Severity of bleeding event assessed by WHO bleeding score and BARC bleeding scale

The number and percentages of subjects with bleeding events will be summarized by the highest bleeding score and by treatment group within each baseline platelet count cohort, separately for WHO bleeding score and BARC bleeding scale.

#### 5.4.3.5 Proportion of subjects with a WHO bleeding score $\geq 2$ after randomization and up to 7 days following an elective procedure

Proportion of subjects with a WHO bleeding score  $\geq 2$  after randomization and up to 7 days following an elective procedure, will be summarized by treatment group within each baseline cohort, and by overall treatment groups, regardless of the baseline platelet count cohorts.

A 2-sided 95% CI will be constructed by baseline cohort, and for the overall treatment difference (avatrombopag minus placebo) using normal approximation method for the proportion of subjects with the qualified WHO bleeding score.

Subjects with missing WHO bleeding score will be considered as having a WHO bleeding score  $\geq 2$  in this analysis.

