16.1.1 Protocol and Protocol Amendments

The [final study protocol](#) is provided on the following pages.

Revisions to V6.0: 31 May 2016 (Amendment 03) Date: V7.0: 02 Dec 2016 (Amendment 04)		
Change	Rationale	Affected Protocol Sections
Sample size reduced from approximately 300 subjects to approximately 200 subjects	After consultation with the FDA, it was decided that the current study has reached adequate enrollment to demonstrate the safety and benefit of avatrombopag in reducing the need for platelet transfusion in subjects with thrombocytopenia and liver disease undergoing an elective procedure.	Synopsis – 
 • Number of Subjects • Sample Size Rationale Section 9.3 Section 9.4.3 Section 9.7.2
The secondary endpoint, proportion of subjects with a World Health Organization (WHO) bleeding score ≥ 2 after randomization and up to 7 days following an elective procedure, will be an exploratory endpoint	Given the rare occurrence of bleeding events (less than expected), this endpoint is better suited as an exploratory endpoint.	Synopsis – 
 • Secondary Objectives • Exploratory Objectives • Secondary Endpoints • Exploratory Endpoints • Secondary Efficacy Variable Analyses • Exploratory Efficacy Variables Section 8.2 Section 8.3 Section 9.7.1.1 Section 9.7.1.6

Revisions to V5.0: 22 June 2015 (Amendment 02) Date: V6.0: 31 May 2016 (Amendment 03)		
Change	Rationale	Affected Protocol Sections
Clarification to Inclusion Criteria #3: replace the word "change" with the word "increase"	Per FDA request	Synopsis – 
• Inclusion Criteria Section 9.3.1

REVISION HISTORY

Revisions to V4.0: 12 Nov 2013 (Amendment 01) Date: V5.0: 22 June 2015 (Amendment 02)		
Change	Rationale	Affected Protocol Sections
Revised the risk of bleeding associated with procedures	Additional procedures included in the source article (Malloy et al., 2009) that originated the initial classification were added. Ongoing study observations, supported by key opinion leader (KOL) review and current literature review resulted in additional updates in the bleeding risk categories classification	Synopsis – 
 • Study Design • Statistical Methods • Efficacy Analyses Section 9.1.2.3 
 • Table 1 Section 9.7.1.6

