## **5.6 SAFETY ANALYSES**

All safety analyses will be performed on the Safety Analysis Set. Unless specified, all safety assessments will be summarized both overall (regardless of baseline platelet count) and within each baseline platelet count cohort. Safety data, presented by treatment group, will be summarized on an “as treated” basis using descriptive statistics or frequency count.

Study Day 1 for all safety analyses is defined as the date of the first dose of study drug. Unless specified otherwise, the baseline value will be defined as the most recent value reported prior to the first dose of study drug.

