### 5.6.6 Other Safety Analyses

#### 5.6.6.1 Adverse Events of Special Interest

The incidence of treatment-emergent adverse events and treatment-related, treatment-emergent adverse events of special interest will be summarized by treatment group.

Adverse events of special interest include:

- Recurrence of thrombocytopenia (platelet count of  $<10 \times 10^9/L$  and  $10 \times 10^9/L$  less than baseline count within 30 days of discontinuation)
- Thromboembolic events
- Bleeding events (WHO Grade 2 to 4)

Recurrence of thrombocytopenia events include the adverse events with MedDRA preferred term belonging to 2nd level Standardized MedDRA Query (SMQ) 'Haematopoietic thrombocytopenia' and with 'Event of Special Interest per Protocol Definition' checked as 'Yes' on the AE CRF page.

Thromboembolic events include the adverse events with MedDRA preferred term belonging to SMQ 'Embolic and thrombotic events'.

Bleeding events (WHO Grade 2 to 4) include the adverse events with MedDRA preferred term belonging to 2nd level SMQ 'Haemorrhage terms (excl laboratory terms)' and with WHO Bleeding Scale score 2 to 4.

Additionally the incidence of treatment-emergent adverse events and treatment-related, treatment-emergent adverse events for thromboembolic events will be summarized by treatment group and by HCC status.

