## 8 DEFINITIONS AND CONVENTIONS FOR DATA HANDLING

### 8.1 VISIT WINDOW

Study Day 1 is defined as the date of the first dose of study drug. The analysis visits defined below will be used in the by-visit summaries:

Visit	Target Visit Date	Visit Window	Analysis Visit
Visit 2 (Baseline)	Study Day 1	Less or equal to Study Day 1	Last visit on or before Study Day 1
Visit 3	Study Day 4	Study Day 2 to 7	Closest visit to Study Day 4
Visit 4	Study Day	Subjects with procedure:	Subjects with platelet

Visit	Target Visit Date	Visit Window	Analysis Visit
(Procedure Day)	10 to 13	Study Day 8 to actual procedure day  Subjects without procedure: Study Day 8 to 13	transfusion: last visit before transfusion  Subjects with procedure but without transfusion: last visit before procedure  Subjects without platelet transfusion or procedure: closest visit to Study Day 10
Visit 5	7 Days post procedure	Subjects with procedure: 1 to 10 days post actual procedure day  Subjects without procedure: Study Day 14 to 20	Subjects with procedure: visit closest to 7 days post actual procedure day  Subjects without procedure: closest visit to Study Day 17
Visit 6	Study Day 35	Subjects with procedure: Greater or equal to actual procedure day +11 days  Subject without procedure: Greater or equal to Study Day 21	Closest visit to Study Day 35

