## 8.2 MISSING DATA HANDLING

For the responder analysis of primary and secondary efficacy endpoints, subjects without the required platelet transfusion data or platelet count data will be considered as non-responders. For other efficacy analyses, unless specified otherwise, observed data will be used without missing data imputation. Details can be found in [Sections 5.4](#), Efficacy Analyses.

Safety data will be analyzed using observed data with no imputation for missing values.

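### The normal-approximation interval planned for WHO bleeding score ≥2 (SAP 5.4.3.5) can under-cover or have zero width when events are few; the endpoint is exploratory

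*SAP*

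**What the plan says.** SAP 5.4.3.5 summarises the proportion with a WHO score of 2 or more, from randomization to 7 days after the procedure, by arm within each cohort and overall. On the interval it says: "A 2-sided 95% CI will be constructed by baseline cohort, and for the overall treatment difference (avatrombopag minus placebo) using normal approximation method". It does not say whether the cohort interval is for each arm's proportion or for the difference, and it names no continuity correction. On missing data: "Subjects with missing WHO bleeding score will be considered as having a WHO bleeding score" of 2 or more.

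The Protocol's Amendment 04 table explains why the endpoint was moved from secondary to exploratory: "Given the rare occurrence of bleeding events (less than expected), this endpoint is better suited as an exploratory endpoint".

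Two other bleeding summaries are planned:

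- **SAP 5.4.3.4** tabulates subjects by highest WHO score, by arm within cohort. It is an efficacy analysis, so it uses the Full Analysis Set and, by the default in SAP 8.2, observed data. It states no time window, no overall row and no interval.
- **SAP 5.6.6.1** tabulates bleeding adverse events selected by a MedDRA query "and with WHO Bleeding Scale score 2 to 4". SAP 5.6 says "All safety analyses will be performed on the Safety Analysis Set", and SAP 8.2 says "Safety data will be analyzed using observed data with no imputation for missing values". These are treatment-emergent events up to 30 days after the last dose, and no interval is given.

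**The concern.** A normal approximation is least reliable when counts are near zero, which is what the sponsor's own rationale leads one to expect. An uncorrected Wald interval then takes its variance from an arm with no events, treats that variance as zero, and comes out too short. If neither arm has an event, the table would show a difference of 0.0 with limits 0.0 and 0.0, although about 100 subjects per cohort cannot exclude differences of several percentage points.

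This is the only between-arm interval planned for WHO ≥2 bleeding, so it is the one a reader would use to judge whether avoiding transfusion costs anything in bleeding. In addition, missing scores are counted as events and 5.4.3.5 shows no observed result beside them, so its result would not show how many of the counted events were actually seen.

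**Working it through.** **Inputs.** Arm sizes come from SAP 4: 67/33 per cohort and 133/67 overall. The documents give neither a bleeding rate nor a missing rate, so 1% to 5% per arm is assumed. Rates are written avatrombopag vs placebo, with none missing unless stated.

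**The plan's own figure.** The SAP gives no figure for this interval. The arm sizes rest on a stated power above 90% for the primary endpoint (53% vs 18%, Fisher's exact test). Exact enumeration gives 92.6%, which agrees.

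**Method.** Uncorrected Wald interval: d ± 1.96 × √[p̂₁(1−p̂₁)/n₁ + p̂₂(1−p̂₂)/n₂]. Coverage is the sum of the binomial probabilities of all outcome pairs whose interval contains the true difference.

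**1. No events in either arm.** With 0/67 vs 0/33:

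- Wald: 0.0 to 0.0
- Newcombe: −10.4 to 5.4 points
- Miettinen-Nurminen: −10.5 to 5.5 points

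The probability of this outcome is (1−p₁)^67 × (1−p₂)^33. At 1% in both arms it is 0.99^100 = 36.6%; at 2% it is 0.98^100 = 13.3%. Overall it is 0.99^200 = 13.4% and 0.98^200 = 1.8%.

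**2. Wald coverage of the difference.**

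| Assumed rates | Cohort 67/33 | Overall 133/67 |
|---|---|---|
| 1% vs 3% | 63% | 86% |
| 2% vs 4% | 74% | 92% |
| 3% vs 1% | 90% | 97% |
| 4% vs 2% | 94% | 96% |
| 1% vs 1% | 99.6% | 98% |
| 2% vs 2% | 98% | 92% |
| 3% vs 3% | 94% | 91% |
| 5% vs 5% | 91% | 93% |

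At equal rates a zero-width interval at 0 counts as covering, which raises those figures. Newcombe gives 99% (cohort) and 98% (overall) at 1% vs 3%, and 96% to 99.8% across the settings tried.

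**3. Why 1% vs 3% does badly.** The true difference is −2.0 points. When placebo has no event, the lowest Wald limit in a cohort arises at 1/67 vs 0/33, where it is −1.41 points. So every such outcome misses. Its probability is 0.97^33 = 36.6%, nearly all of the 100 − 63.2 = 36.8% non-coverage. Overall, 0.97^67 = 13.0% accounts for nearly all of the 13.6%.

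**4. With a continuity correction.** This adds (1/n₁ + 1/n₂)/2 to each side.

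- Cohort: 2.3 points. 0/67 vs 0/33 gives ±2.3, and coverage at 1% vs 3% becomes 99.8%.
- Overall: 1.12 points. With no placebo event the lowest uncorrected limit, at 1/133, is 0.75 − 1.47 = −0.72. Corrected it is −1.84, still short of −2.0, so coverage stays at 87%.

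**5. If the cohort interval is for single arms.** At true rates of 1%, 2% and 3%, Wald coverage is 28%, 49% and 63% for n = 33, and 49%, 74% and 87% for n = 67. Wilson gives 92% to 97%.

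**6. Effect of the missing-as-event rule.** The counted rate is p(1−m) + m.

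- With equal missingness the difference shrinks by the factor (1−m): −2.0 becomes −1.9 points at 5%.
- At 1% vs 3% with 1%, 2% and 5% missing in both arms, Wald coverage of the counted difference is 73%, 81% and 91% (cohort) and 92%, 93% and 94% (overall).
- At 1% vs 1% with 1% missing, the counted rate is 0.01 × 0.99 + 0.01 = 0.0199, and the cohort zero-width probability falls to 0.9801^100 = 13%.
- At a true 2% with 5% missing, the counted rate is 0.02 × 0.95 + 0.05 = 6.9%, of which 5/6.9 = 72% is imputed.
- One imputed subject moves a cohort difference by 1/33 = 3.0 points (placebo) or 1/67 = 1.5 points (avatrombopag).

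**7. Can the other tables replace an observed-score result?** SAP 5.4.3.4 has the right analysis set and instrument. However, it states no window, and Protocol Table 5 continues bleeding assessment to Visit 6. For subjects with a procedure, SAP 8.1 places Visit 6 at "Greater or equal to actual procedure day +11 days", outside the 7-day window. SAP 5.6.6.1 differs in analysis set, event selection and window.

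**The case against.** Four points on the other side have force.

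- **The method is not fully named.** A continuity-corrected interval is also a normal approximation, and it removes the zero width and the poor cohort coverage. That stands, so those results are conditional on the uncorrected reading. It does not clear the plan: the SAP names no correction, and overall coverage at 1% vs 3% hardly moves.
- **The worst figures assume no imputed events.** One missing score is enough to remove the zero width, and 5% missing largely restores coverage. That stands too, but what is then covered is a difference partly made of imputed events.
- **The shortfall runs mainly one way.** It is largest when placebo bleeds more. At reversed or equal rates the interval does much better, and the overall interval loses less than the cohort ones.
- **An observed table already exists.** Adding grades 2 to 4 in SAP 5.4.3.4 gives an observed count by arm and cohort. That reduces the second complaint to the missing 7-day window, the missing overall row and the missing count of imputed events.

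A reader might go further and infer that the missing-as-event rule biases the comparison. The documents do not support this. The rule follows the same convention as the primary endpoint, where subjects with missing outcomes "will be considered as having received a transfusion for the primary analysis", and as the first secondary endpoint. It biases the difference beyond the (1−m) shrinkage only if missingness differs between arms, and nothing in the documents suggests that it will.

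**Conclusion.** The point holds in conditional form and is a matter to consider, not a threat to the trial. If normal approximation means uncorrected Wald and few scores are imputed, the interval has zero width when no event is counted in either arm. At assumed rates of 1% vs 3% it covers 63% of the time per cohort and 86% overall; read as a single-arm interval at n = 33 it covers 28% to 63% at rates of 1% to 3%.

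It would be too strong to say that the planned interval will have 63% coverage. That figure needs an assumed rate pair in one direction, no correction and no imputed events. It would also be too strong to say that no observed WHO-score analysis is planned. SAP 5.4.3 marks this analysis as exploratory and 5.4.3.5 attaches no test to it, so the primary and secondary conclusions do not depend on it.

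**What to change.** In SAP 5.4.3.5:

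1. Replace the normal approximation with a Newcombe or Miettinen-Nurminen score interval for the treatment difference, by cohort and overall. Use Wilson if the cohort interval is meant for single arms, and say which is meant.
2. As a minor addition, show beside the missing-as-event result the number of imputed events per arm and the observed-score proportion on the same window (randomization to 7 days after the procedure), by cohort and overall. The observed-score result assumes that missingness is unrelated to bleeding, so the two should be read together.

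The cost is two SAP sentences, a standard software option and one extra display. The intervals will be wider: at 1% vs 3% the mean width is 18.8 points for Newcombe against 10.6 for Wald per cohort, and 11.3 against 8.3 overall. Newcombe is also somewhat conservative at these rates. That width is a fair picture of how little a few events can show.
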